## 2.4. Statistical Hypotheses / Statistical Analyses

The primary objective of this study is to evaluate the efficacy and safety of UMEC in combination with FF/VI in participants with asthma over a 24-week treatment period. This is a superiority study to demonstrate the add-on benefit of UMEC at two dosage strengths 62.5 mcg and 31.25 mcg in a single inhaler when compare to FF/VI. The primary efficacy endpoint is the mean change from baseline in trough FEV1 at the end of the 24-week treatment period.

For each test on each efficacy endpoint, the null hypothesis is that there is no difference between treatment groups.

$$H_0: T_1 - T_2 = 0$$

The alternative hypothesis is that there is a difference between treatment groups.

$$H_1: T_1 - T_2 \neq 0$$

For the primary endpoint and other lung function related efficacy endpoints, the primary treatment comparisons of interest are the comparisons for each triple therapy and the respective dual therapy FF/VI without the UMEC component as follows:

UMEC 62.5 mcg:

- FF/UMEC/VI 100/62.5/25 mcg vs. FF/VI 100/25 mcg
- FF/UMEC/VI 200/62.5/25 mcg vs. FF/VI 200/25 mcg

UMEC 31.25 mcg:

- FF/UMEC/VI 100/31.25/25 mcg vs. FF/VI 100/25 mcg
- FF/UMEC/VI 200/31.25/25 mcg vs. FF/VI 200/25 mcg

Therefore, T1 and T2 for these endpoints are the mean changes from baseline for the individual triple therapy and dual therapy, respectively, as listed above.

For the key secondary endpoint and all other non-lung function efficacy endpoints, the primary treatment comparisons of interest are the comparisons between triple therapy and dual therapy for a fixed dose of UMEC:

- (FF/UMEC/VI 100/62.5/25, 200/62.5/25) vs. (FF/VI 100/25, 200/25)
- (FF/UMEC/VI 100/31.25/25, 200/31.25/25) vs. (FF/VI 100/25, 200/25)

For example, T1 and T2 in the hypothesis associated with the key secondary efficacy endpoint are the averages of the mean annualized rate of moderate/severe exacerbations for the triple therapies over two FF doses at a given UMEC dose, and for the dual therapies over two FF doses, respectively.

### 3. PLANNED ANALYSES

#### 3.1. Interim Analyses

No interim analysis is planned for this study.

#### 3.2. Final Analyses

The final planned primary analyses will be performed after the completion of the following sequential steps:

1. All participants have completed the study as defined in the protocol.
2. All required database cleaning activities have been completed and final database release (DBR) has been declared by Data Management (DM).
3. System Independent (SI) data to Study Data Tabulation Model (SDTM) data conversion has completed by Conversion Service Provider at Source Data Lock (SDL).
4. All criteria for unblinding the randomization codes have been met. Randomization codes have been distributed according to RandAll NG procedures. Release of randomization code and treatment container list, unblinding of study treatment and participant level treatment of SDTM data, and related quality control activities have been completed by Statistics and Programming (S&P).
5. Database freeze on SDTM datasets has been declared by DM upon receipt of the final, treatment unblinded SDTM data from S&P.

### 4. ANALYSIS POPULATIONS

Population	Definition / Criteria	Analyses Evaluated
All Subjects Enrolled	
 
• This population will comprise all participants for whom a record exists on the study database, including pre-screened participants that sign the informed consent document but do not complete a Visit 1 (screening) procedure (i.e., pre-screening failures), or participants that complete at least one Visit 1 procedure but do not enter the run-in period (i.e., screening failures).
 
	
 
• Study Population
 

All Subjects Screened	
 
• This population contains all participants that complete at least one Visit 1 (Screening) procedure
 
	
 
• Study Population
 
• Adverse events for non-ITT participants
 

Randomized	
 
• This population will comprise of all participants who were randomized (i.e. received a randomization number)
 
	
 
• Study population
 

Intent-to-Treat (ITT)	
 
• This population will comprise all randomized participants, excluding those who were randomized in error. A participant who is
 
	
 
• Study population
 
• Efficacy
 
• Safety
 

Population	Definition / Criteria	Analyses Evaluated
	recorded as a screen failure, run-in failure, or stabilisation failure, but is randomized and does not receive a dose of study treatment, is considered to be randomized in error.	
 
• Health outcomes
 

Pharmacokinetic	
 
• This population will comprise all participants in the ITT Population for whom a PK sample was obtained and analysed.
 
	
 
• PK
 

Refer to [Appendix 10](#): List of Data Displays which details the population used for each display.

## 5. CONSIDERATIONS FOR DATA ANALYSES AND DATA HANDLING CONVENTIONS

### 5.1. Study Treatment & Sub-group Display Descriptors

Treatment Group Descriptions				
RandAll NG		Data Displays for Reporting		
Code	Description	Description	Displays	Order in TFL
1	FF/VI 100/25 QD	FF/VI 100/25	FF/VI 100/25	1
2	FF/VI 200/25 QD	FF/VI 200/25	FF/VI 200/25	4
3	FF/UMEC/VI 100/31.25/25 QD	FF/UMEC/VI 100/31.25/25	FF/UMEC/VI 100/31.25/25	2
4	FF/UMEC/VI 200/31.25/25 QD	FF/UMEC/VI 200/31.25/25	FF/UMEC/VI 200/31.25/25	5
5	FF/UMEC/VI 100/62.5/25 QD	FF/UMEC/VI 100/62.5/25	FF/UMEC/VI 100/62.5/25	3
6	FF/UMEC/VI 200/62.5/25 QD	FF/UMEC/VI 200/62.5/25	FF/UMEC/VI 200/62.5/25	6
7*	N/A	FF/VI 100/25 or 200/25	FF/VI	7
8*	N/A	FF/UMEC/VI 100/31.25/25 or 200/31.25/25	FF/UMEC/VI UMEC 31.25	8
9*	N/A	FF/UMEC/VI 100/62.5/25 or 200/62.5/25	FF/UMEC/VI UMEC 62.5	9

**NOTES:**

\*: applicable only to the displays based on the pooled analysis.

The details on the treatment comparisons of interest are provided in Section 7.

## 5.2. Baseline Definition & Derivations

For clinic FEV1, the Baseline value is the last acceptable/borderline acceptable pre-dose FEV1 prior to randomized treatment start date (either from pre-dose at Day 1 or pre-bronchodilator at Enrolment Visit or at an unscheduled visit which occurs between the Enrolment Visit and Day 1).

For ACQ, SGRQ, and AQLQ, baseline value for each endpoint is the derived value based on the questionnaire administered at the randomization visit.

For the safety assessments of clinical laboratory, vital signs, and ECGs, the baseline value is the latest value recorded prior to first dose, including pre-dose unscheduled visits.

For diary data the baseline is the average value over the last 14 days prior to randomized treatment start (for more details see Section 5.3.2). If fewer than 7 days of data over the baseline period are available, the baseline value will be set as missing.

If time is not collected, Day 1 clinic assessments (or Day 1 AM diary assessments) are assumed to be taken prior to first dose and used in the derivation for baseline.

All baselines will be referred to as ‘Baseline’ in the summary outputs.

Parameter	Study Assessments Considered as Baseline	
Clinic Assessments		
	Screening	Day 1 (Pre-Dose)
Efficacy		
Trough FEV 1 , FEV 1 3h post study treatment		X*
ACQ-5, ACQ-6, ACQ-7, SGRQ, AQLQ, Global Assessment of Severity		X
Safety		
Clinical Laboratory (incl. total serum IgE and FeNO) †	X	
ECGs†	X	
Vital signs†		X
Diary Assessments		
	Baseline Period	
Efficacy		
Home Daily Trough FEV 1 , Home Daily AM PEF	Last 14 AM assessments during the stabilisation period, including AM assessment on the day of first treatment, prior	

Parameter	Study Assessments Considered as Baseline
	to first dose (i.e., treatment start date per protocol)
Home Daily PM FEV 1 , Home Daily PM PEF	Last 14 PM assessments immediately preceding first treatment during the stabilisation period
%Symptom free days, % rescue medication free days, daily rescue medication use	Last 14 days during the stabilisation period, including AM assessments on the day of treatment i.e., treatment start date per protocol).
E-RS total score and domain scores	Last 14 PM assessments immediately preceding first treatment date during the stabilisation period

\*: last acceptable/borderline acceptable (pre-dose) FEV1 value obtained prior to treatment (either from pre-dose at Visit 3 (Randomization) or from pre-bronchodilator at Visit 2 or unscheduled assessments between Visit 2 and Visit 3).

† latest value taken prior to first dose including pre-randomized treatment unscheduled visits.

Unless otherwise stated, if baseline data is missing no derivation will be performed and baseline will be set to missing.

For participants that did not receive any randomized study treatment, baseline is defined as the value from the protocol schedule baseline visit. Unscheduled visits will not be considered.

### **5.3. Change from Baseline Definitions and Derivations**

#### **5.3.1. Clinic Assessments**

For any efficacy and safety endpoint based on clinic assessment, the change from baseline value at a given clinic visit is the value at the clinic visit minus the baseline value.

Maximum increase from baseline is the maximum on-treatment value over all timepoints – baseline value.

Maximum decrease from baseline is the minimum on-treatment value over all timepoints – baseline value.

### 5.3.2. Diary Assessments

Day 1 of post-randomization diary data consist of PM assessment on Day 1 (the day of Randomization Visit) and AM assessment on the day after Randomization Visit. Similarly, for any given day, daily assessments consist of the PM assessment on that day and the AM assessment the day after.

The periods over the 52 weeks with 4-week time intervals are defined as follows:

Weeks	AM assessment Days	PM assessment / E-RS Days	Rescue medication use/ Symptoms free days
Weeks -2 and -1 (Baseline)	-13 to 1	-14 to -1	PM day -14 to AM day 1
1-4	2-29	1-28	PM day 1 to AM day 29
5-8	30-57	29-56	PM day 29 to AM day 57
9-12	58-85	57-84	PM day 57 to AM day 85
13-16	86-113	85-112	PM day 85 to AM day 113
17-20	114-141	113-140	PM day 113 to AM day 141
21-24	142-169	141-168	PM day 141 to AM day 169
25-28	170-197	169-196	PM day 169 to AM day 197
29-32	198-225	197-224	PM day 197 to AM day 225
33-36	226-253	225-252	PM day 225 to AM day 253
37-40	254-281	251-280	PM day 251 to AM day 281
41-44	282-309	281-308	PM day 281 to AM day 309
45-48	310-337	309-336	PM day 309 to AM day 337
49-52	328-365	327-364	PM day 327 to AM day 365
1-24	2-169	1-168	PM day 1 to AM day 169

For any given period (e.g., over a 4-week period), the value for a given diary endpoint is calculated using all available data as the average of the non-missing daily values over that period. If fewer than 14 days of data are available over a 4-week period, the period value will be set as missing. In general, if the data are available for fewer than 50% of the days

in the period, the period value will be set as missing. The change from baseline over that period will be calculated as the participant's period value minus the baseline value.

For the purpose of efficacy analyses and summaries based on diary data, data collected outside of the defined periods will be excluded.

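### SAP 5.3.2: misprinted start days make the Weeks 37-40 (PM and rescue/symptom columns) and Weeks 49-52 (all columns) diary windows too long and overlapping

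*SAP*

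**What the plan says.** SAP 5.3.2 introduces its table with the sentence "The periods over the 52 weeks with 4-week time intervals are defined as follows". The table has three columns: AM assessment days, PM assessment/E-RS days, and the combined rescue-use and symptom-free-day window. The columns are linked by the rule that "for any given day, daily assessments consist of the PM assessment on that day and the AM assessment the day after".

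The rows at issue, with their predecessors in the rescue/symptom column, are:

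- Weeks 33-36: "PM day 225 to AM day 253", followed by Weeks 37-40: "PM day 251 to AM day 281".
- Weeks 45-48: "PM day 309 to AM day 337", followed by Weeks 49-52: "PM day 327 to AM day 365".

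A period value is "calculated using all available data as the average of the non-missing daily values over that period". On missing data, "If fewer than 14 days of data are available over a 4-week period, the period value will be set as missing". A general rule then sets a period to missing when under half of its days have data. The section closes by excluding diary data that fall outside the defined periods, so the table governs the derivation directly.

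**The concern.** Two rows start before the preceding row has ended. A programmer who follows the table literally would put the same diary days into two successive period values and would report as a 4-week value something that covers more than four weeks. The missing-data rule would also become ambiguous, because 14 days is half of 28 days but not half of 30 or 38.

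At stake are the 4-weekly summaries to Week 52 in SAP 11.10.6:

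- E-RS total score: Tables 2.75 and 2.78
- home trough and PM FEV1: Tables 2.84 and 2.88
- AM and PM PEF: Tables 2.91 and 2.94
- E-RS domains: Table 2.115
- symptom-free days, rescue-free days and rescue use: Tables 2.124, 2.127 and 2.130

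The E-RS box and distribution plots in SAP 11.10.7 (Figures 2.50, 2.51, 2.56 and 2.57) use the same windows.

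**Working it through.** **Inputs.** All day numbers come from the table in SAP 5.3.2.

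**Rule implied by the table.** Number the post-baseline rows k = 0 to 12. A consecutive 28-day scheme gives:

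- PM/E-RS: day 1 + 28k to day 28 + 28k
- AM: day 2 + 28k to day 29 + 28k
- Rescue/symptom: PM day 1 + 28k to AM day 29 + 28k

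Eleven of the thirteen rows match this in every column. For example, Weeks 21-24 (k = 5) gives PM 141-168 and AM 142-169, as printed. The Weeks 1-24 row also checks: 169 - 2 + 1 = 168 AM days and 168 PM days, and 24 x 7 = 168.

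**Lengths and overlaps.** In the AM and PM columns, length = end - start + 1. In the rescue/symptom column, diary days = AM end - PM start.

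| Row, column | Printed | Length | Previous window ends | Overlap | Rule gives |
|---|---|---|---|---|---|
| 37-40, AM | 254-281 | 28 | 253 | 0 | 254-281 |
| 37-40, PM/E-RS | 251-280 | 280 - 251 + 1 = 30 | 252 | 2 (251-252) | 253-280 |
| 37-40, rescue/symptom | PM 251 to AM 281 | 281 - 251 = 30 | AM 253 | 253 - 251 = 2 | PM 253 to AM 281 |
| 49-52, AM | 328-365 | 365 - 328 + 1 = 38 | 337 | 10 (328-337) | 338-365 |
| 49-52, PM/E-RS | 327-364 | 364 - 327 + 1 = 38 | 336 | 10 (327-336) | 337-364 |
| 49-52, rescue/symptom | PM 327 to AM 365 | 365 - 327 = 38 | AM 337 | 337 - 327 = 10 | PM 337 to AM 365 |

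**Column totals.** Fifty-two weeks is 364 days. As printed, AM gives 12 x 28 + 38 = 374. PM/E-RS and rescue/symptom each give 11 x 28 + 30 + 38 = 376.

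**Share of each window that belongs to the previous period.** Weeks 49-52: 10/38 = 26%. Weeks 37-40 (PM/E-RS and rescue/symptom): 2/30 = 7%.

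**Effect on a period mean with complete data.** Let A be the mean over the 10 overlapping days and B the mean over the correct 28 days. The printed window gives (10A + 28B)/38, which differs from B by (10/38)(A - B), about 0.26 of the difference between the two stretches. For Weeks 37-40 the factor is 2/30, about 0.07. The documents give no values for A and B, so the shift in any reported mean cannot be stated.

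**Missing-data rule.** Fourteen days is 14/28 = 50% of a correct window, but 14/30 = 46.7% and 14/38 = 36.8% of the printed ones. The specific rule therefore asks for 14 days, while the general rule asks for 15 of 30 or 19 of 38. SAP 11.6.3 applies its own 50% rule to symptom-free and rescue-free days.

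As an example, take a participant whose AM diary is complete to day 341 and then stops. The printed window holds days 328-341, which is 14 days: this passes the 14-day rule and fails the 50% rule. The correct window holds only days 338-341, which is 4 days, so the value should be missing under either rule.

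**The case against.** The strongest reply is that this is an obvious typing slip with little reach. The section says the intervals are four weeks long, every other row advances by 28 days, and a programmer or a quality check would probably notice. No planned model uses the affected windows: the E-RS model in SAP 7.3.5.1 stops at Weeks 21-24, the other diary endpoints in SAP 7.4.4.1 follow it, and the E-RS tests at Levels 9 and 10 of the hierarchy use Weeks 21-24.

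Few participants reach these periods. Under SAP 11.3.2 only those randomized on or before 6 May 2017 had a planned Week 52 end of study. Someone finishing at Week 36 on schedule (target day 253, window -5/+2 days) would contribute at most PM days 251-255 to Weeks 37-40, and the 14-day minimum would set that value to missing. No day is counted twice within a single period value, and the conflict between the two missing-data thresholds follows from the same misprint.

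All of that stands, and it limits the importance of the point. It does not remove the error. The misprinted starts agree across columns, so a fault in reading the file is unlikely. Nothing elsewhere in the SAP corrects them, and the section makes these windows the derivation rule. Relying on someone to notice is not a specification.

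**Conclusion.** The table is wrong as printed in five cells. Weeks 49-52 are 38 days with a 10-day overlap in all three columns. Weeks 37-40 are 30 days with a 2-day overlap in the PM/E-RS and rescue/symptom columns only, so home trough FEV1 and AM PEF are affected in Weeks 49-52 alone.

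The consequence is confined to ten descriptive tables and four E-RS figures that run past Week 24. No hypothesis test, model, power figure or error-rate statement changes. The only assumption is that consecutive 28-day windows were intended, which the section's own wording and the other eleven rows support. This is a minor correction, worth making because a literal reading gives wrong period values and two competing missing-data thresholds.

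**What to change.** Correct five start days in the SAP 5.3.2 table and leave every end day as it is:

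- **Weeks 37-40:** PM/E-RS days 253-280; rescue/symptom PM day 253 to AM day 281.
- **Weeks 49-52:** AM days 338-365; PM/E-RS days 337-364; rescue/symptom PM day 337 to AM day 365.

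Every 4-week window is then 28 days, none overlap, each column totals 364 days, and the 14-day and 50% rules agree again. The cost is an edit to one table and a check that the diary derivation program uses the corrected limits. No further data or analyses are needed.

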#### 5.4. Multi-Centre Studies

Due to the large number of centers participating in this study, a geographical region will be used rather than adjusting for center in the statistical analyses. The center grouping will be created based on geographical region and number of randomized participants in a country, in order to define groups of roughly similar size.

Geographic Region	Countries	Total # Randomized / Planned
Europe	Germany, Italy, Netherlands, Poland, Romania, Spain, United Kingdom,	766 / 575
Russia	Russian Federation	643 / 500
United States	United States	399 / 400
Rest of World	Argentina, Australia, Canada, Japan, Republic of Korea, South Africa	631 / 735

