12.7. Appendix 7 Country Specific Requirements

12.7.1. Country Specific Requirement for the Randomization of Subjects

Japan Only: Subjects will be stratified by pre-study ICS treatment dosage strength (mid, high) at screening and will be assigned to study treatment in accordance with a country-specific randomization schedule (to ensure treatment balance within each stratum (mid- or high-dose pre-study ICS treatment dosage strength). The randomization code will be generated by GSK using a validated computerized system. Subjects will be randomized using an IRT system (RAMOS NG). Once a randomization number is assigned to a subject it cannot be reassigned to any other subject in the study.

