## 2. SUMMARY OF KEY PROTOCOL INFORMATION

### 2.1. Changes to the Protocol Defined Statistical Analysis Plan

Changes from the planned statistical analysis specified in the protocol are outlined in the table below. In addition, in order to comply with regulatory guidance where the protocol referred to “Subjects” the analysis plan refers to “Participants”, with the exception of displays and study populations.

Protocol	Reporting & Analysis Plan	
Statistical Analysis Plan	Statistical Analysis Plan	Rationale for Changes
Key secondary endpoint: The pooled analysis was to include the pooled (FF doses) 3-arm data and the FF dosage as a (categorical) covariate in the analysis model.	Key secondary endpoint: The pooled analysis will include all 6-arm data in the model. The treatment effect (pooled over FF doses) will be estimated using LSMESTIMATE statement in SAS PROC GENMOD.	This change is to ensure a consistent analysis method for pooled analyses (FF doses) in the CSR and the pooled analyses (FF doses, UMEC doses, FF and UMEC doses) planned for the submission (SDAP). The method proposed in the protocol for pooled (FF doses) analysis cannot be applied for the pooled (UMEC doses, FF and UMEC doses) analyses in SDAP due to study design.
Region was not included as a covariate for the proposed primary and key secondary analysis.	Region is added as a covariate for all statistical analysis models.	The study is a global study with 15 participating countries across multiple regions. The change is to ensure that the statistical analysis adjusts for possible region effect due to differences in local medical practices in the treatment of asthma.
Exacerbation history was not included as a covariate in the proposed statistical analysis for the key secondary endpoint.	The severe asthma exacerbations in the previous year (0, 1, >=2) is added as a covariate for all asthma exacerbation related analyses.	This change is to ensure that the exacerbation analysis is adjusted for asthma severity based on exacerbation history.
No mention of a randomized	Defines a randomized	In order for the randomized

Protocol	Reporting & Analysis Plan	
Statistical Analysis Plan	Statistical Analysis Plan	Rationale for Changes
population	population	population to be included in the summary of analysis populations and so clearly show the flow of participants through the study, see Section 4.

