Treatment Assignment	
 
• Eligible participants will enter a 3-week run-in period on fluticasone/salmeterol [FSC], 250/50 mcg twice a day via the DISKUS DPI, followed by a 2-week stabilization period on FF/VI 100/25 mcg via the ELLIPTA DPI once a day in the morning.
 
• At the conclusion of the stabilisation period, eligible participants are to be randomized 1:1:1:1:1:1 to receive one of the following six double-blind study treatments: 
 
○ FF/UMEC/VI 100/62.5/25 mcg
 
○ FF/UMEC/VI 200/62.5/25 mcg
 
○ FF/UMEC/VI 100/31.25/25 mcg
 
○ FF/UMEC/VI 200/31.25/25 mcg
 
○ FF/VI 100/25 mcg
 
○ FF/VI 200/25 mcg
 
 
 
• The randomization code will be generated using GlaxoSmithKline (GSK) software (RANDALL NG) and stratified by pre-study ICS dosage at screening. The study will use one central randomization schedule to allocate treatments for all randomized participants except those from Japan. A separate randomization schedule will be generated for Japan to ensure the treatment balance in a total number of approximately 300 randomized participants for the country specific requirement.
 
• Participants will be randomized using an IRT system (RAMOS NG).
 

Interim Analysis	
 
• No interim analysis is planned for this study.
 

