#### 5.5. Examination of Covariates, Other Strata and Subgroups

##### 5.5.1. Covariates and Other Strata

Covariates will be included in statistical analyses as detailed in the statistical model specifications in Section 7.

The covariates to be included in the primary analysis model are sex, age, region, pre-study ICS dosage at screening and baseline FEV1. A summary of significance levels for the main effects from the primary analysis model and their interactions with treatment will be provided, see Section 7.1.5 for details.

The rationale for including each of these covariates are as follows:

- Sex and age are known to be strongly associated with lung function (Quanjer 2012).
- Region will account for any differences in background standard of care between regions. In particular, due to a high proportion of participants from Russia, the inclusion of region will help ensure the results are applicable across all regions.
- Inclusion of Baseline as a covariate is standard statistical practice, and recommended by the EMA guidance, Points to Consider on Adjustment for Baseline Covariates.
- Inclusion of the stratification variable pre-study ICS dosage at screening as a covariate is recommended by ICH-E9 (Statistical Principles for Clinical Trials). The actual strata a participant belongs to, as indicated in the eCRF will be used for this covariate, regardless of mis-stratification.

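### Japan is randomized from its own schedule, but the region factor merges it into Rest of World, so the models reflect that stratum only in part; the cost is slight conservatism, not bias

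*SAP*

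**What the plan says.** Protocol 12.7.1 (Appendix 7) provides that Japanese subjects are stratified by mid or high pre-study ICS dose and "will be assigned to study treatment in accordance with a country-specific randomization schedule". SAP 2.3 describes the other side: "The study will use one central randomization schedule to allocate treatments for all randomized participants except those from Japan". It gives the purpose and planned size of the Japanese schedule: "A separate randomization schedule will be generated for Japan to ensure the treatment balance in a total number of approximately 300 randomized participants".

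SAP 5.4 defines four regions, with these numbers randomized: Europe 766, Russia 643, United States 399 and Rest of World 631. Rest of World consists of "Argentina, Australia, Canada, Japan, Republic of Korea, South Africa". The grouping uses geography and country size "in order to define groups of roughly similar size". SAP 2.1 then states: "Region is added as a covariate for all statistical analysis models". The region summaries (SAP 5.5.2) use the same four levels, and the treatment-by-region interaction checks (SAP 7.1.6 and 7.2.6) use the same factor.

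On stratification, SAP 5.5.1 says: "Inclusion of the stratification variable pre-study ICS dosage at screening as a covariate is recommended by ICH-E9". It does not mention the Japanese schedule. The only place where the SAP codes Japan separately is the region variable of the population PK dataset (SAP 9.1), which is analysed under another plan.

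**The concern.** Two schedules, each blocked within ICS stratum, make country group (Japan or not) a factor by which the trial randomizes. The SAP justifies the ICS covariate on the ground that ICS dose is a stratification variable. It neither applies that reasoning to the Japanese schedule nor says why it should not.

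When allocation is balanced within a stratum but the model leaves the stratum out, any outcome difference between strata stays in the residual variance although the design has already removed it from the treatment contrast. The reported standard error is then larger than the true sampling error. What is at stake is a little precision, agreement between design and analysis, and the ability of the region displays and interaction checks to show a Japan-specific pattern.

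**Working it through.** **1. The plan's own figure.** Protocol 9.2.1: 337 evaluable per arm, difference 100 mL, SD 400 mL, two-sided alpha 0.05. The standardized effect is 100 / (400 × √(2/337)) = 3.245, so power = Φ(3.245 − 1.960) = 0.9006 (0.8998 with the noncentral t). The stated 90% reproduces, and 337 / 0.90 gives 375 randomized per arm.

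**2. Region sizes (SAP 5.4).** 766 + 643 + 399 + 631 = 2439 randomized. Rest of World is 631/2439 = 25.9%.

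**3. Assumptions.** Japan's number J is not given, so I use 50 to 300. Nor is its difference d in FEV1 change from the other Rest of World countries, so I use 50 to 200 mL. The top of the range for J is the figure still printed in SAP 2.3.

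**4. Trough FEV1.** With p = J/631, the variance left in the residual by merging is (631/2439) × p(1 − p) × d², set against 400² = 160,000.

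| J | d (mL) | Variance left (mL²) | Rise in SE |
|---|---|---|---|
| 50 | 50 | 47 | 0.01% |
| 50 | 200 | 755 | 0.24% |
| 100 | 200 | 1,380 | 0.43% |
| 300 | 100 | 645 | 0.20% |
| 300 | 200 | 2,581 | 0.80% |

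Worked for the last row: p = 300/631 = 0.475; 0.2587 × 0.475 × 0.525 × 40,000 ≈ 2,581; √(1 + 2,581/160,000) = 1.0080.

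**5. Consequence in the last row.**
- Type I error is 2 × [1 − Φ(1.960 × 1.0080)] = 0.0482, below the nominal 0.05.
- Because blocking holds Japan in balance, only the critical value is stretched: power = Φ(3.245 − 1.960 × 1.0080) = 0.898, a loss of 0.3 point.
- Treating the larger SE as the true one gives Φ(3.245/1.0080 − 1.960) = 0.896, a loss of just under 0.5 point.
- A stress case with J = 300 and d = 400 mL (one full SD) gives SE +3.2%, type I error 0.043 and power 88.9%.

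**6. Simulation.** Six arms in permuted blocks of 6 (block size assumed) within Japan × ICS stratum, all 2439 participants, 3,000 runs, J = 300, d = 200 mL.
- With no treatment effect, type I error was 0.049 with four region levels and 0.050 with five. The mean model SE was 28.29 against 28.07, a ratio of 1.008, as in step 4.
- With a true difference of 100 mL, the mean estimate was 99.9 mL under both models and power was 0.939 against 0.941. Power exceeds 90% because no dropout was simulated.
- With J = 100, the two models differed by less than the simulation error.

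**7. Exacerbations.** Protocol 9.2.1 gives dispersion k = 0.7 and a rate of 2 per year. If Japan's rate is a fraction of the other countries', the merged level behaves like a negative binomial with k′ = k + CV²(1 + k), where CV² is the squared coefficient of variation of the rate mixture. Information per participant is 1/(1/m + k) for expected count m.

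- *Upper end:* J = 300, rate halved, one year of follow-up for all, mean Rest of World rate 2. CV² = 0.25 × 0.475 × 0.525 / 0.762² = 0.107 and k′ = 0.88. Merged information is 1/(0.5 + 0.88) = 0.724. Kept separate, the expected counts are 1.31 and 2.62 and the average information is 0.810. The loss is 10.7% within Rest of World and 10.7% × 0.259 = 2.8% overall.
- *Same case, shorter follow-up:* 2.3% overall at 0.7 year and 1.8% at 24 weeks.
- *Middle:* J = 100, rate halved, 0.7 year: about 0.8% to 0.9%.
- *Lower end:* J = 50, rate 25% lower, 24 weeks: about 0.1%.

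These figures ignore the model's other covariates (exacerbation history, age, sex), which may absorb part of a country difference.

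**The case against.** The SAP gives a reason for its grouping, namely similar group sizes, and a Japan level could be small. Europe also pools seven countries. Protocol 6.2 names only pre-study ICS dose as the stratification factor, and the SAP cites ICH E9 only for that factor. The 300 participants in SAP 2.3 match a requirement that Protocol Amendment 3 withdrew, so the larger losses may never arise. Nothing in the documents suggests that Japan's exacerbation rate is half that of its neighbours. Country counts will be tabulated anyway (SAP 6.1, Tables 1.4 and 1.5).

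Much of this stands. The size criterion explains the choice, and with 50 Japanese participants (about 8 per arm) merging would be reasonable. With 300 it would not be forced: the split would be 300 and 331, against 399 in the United States. Europe differs in that none of its countries has its own schedule. No objection shows harm from a fifth level.

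A reader might infer that the analysis ignores Japan, or that the region term fails in its purpose. The documents support neither. Japan is adjusted through its region level and the ICS covariate. SAP 2.1 asks only that a possible region effect be allowed for, and a coarse level still does some of that. A reader might also fear confounding or false positives, but allocation is 1:1:1:1:1:1 both inside and outside Japan.

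**Conclusion.** The point holds as a small gain in efficiency and consistency. Japan is a randomization stratum in effect, and the models reflect it only in part. Treatment estimates are unbiased, and any error in the p-values is on the conservative side. Within the assumed ranges no planned conclusion is likely to turn on it, and the effect is nil if Japan resembles the other Rest of World countries. The sizes rest on assumed values for Japan's number, FEV1 difference and exacerbation rate, because the documents give none of these.

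**What to change.** In SAP 5.4, define region with five levels (Europe, Russia, United States, Japan, Rest of World) and carry this into the efficacy models and region summaries. State Japan's randomized number. If it proves too small for a stable level, keep four levels in the main models, run the five-level model as a sensitivity analysis, and say why. Decide this on blinded data before unblinding; SAP 1.1 already allows analysis decisions up to source data lock. The cost is a few lines of text and one degree of freedom among 2439 participants.

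Separately, reconcile SAP 2.3, which still gives about 300 Japanese participants as a country requirement, with current protocol 12.7.1, which states no number.
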